CC-5013-CLL-009 is a phase 2, multi-center, randomized, double-blind, parallel-group adaptive design study that will evaluate the safety and efficacy of different lenalidomide dose regimens administered orally. All regimens use a stepwise dose escalation scheme with three different initial ascending starting dose of 5 mg daily, 10 mg daily and 15 mg daily and then escalating in a stepwise manner every 28 days to reach a maximum dose of 25 mg daily based on subject tolerability. Approximately 105 subjects will be enrolled. Eligible subjects must have B-cell CLL that has relapsed after or is refractory to at least one prior CLL treatment regimen. At least one of the prior treatments must have included a purine-analog or bendamustine based treatment regimen. Subjects must have active disease per the iwCLL Guidelines for the diagnosis and treatment of CLL (Hallek, 2008).

At the time of randomization, study subjects will be stratified by the following criteria:

- Relapsed vs. refractory to their last purine-analog or bendamustine based treatment regimen [relapsed/refractory as defined per the iwCLL guidelines for diagnosis and treatment of CLL (Hallek, 2008)]. If subject has received both, the status post most recent purine-analog or bendamustine regimen will be used for stratification.
- Age < 65 years of age vs. \ge 65 years of age

Screening

Subjects will sign informed consent prior to undergoing any study-related procedures. Screening assessments for protocol eligibility will be performed within 28 days prior to initiating study drug as outlined in Table 2.

During screening all subjects will have the following assessments / samples collected:

- Vital signs, including height and weight
- Pregnancy testing as specified in Appendix 21.9
- Pregnancy and risk counseling as specified in Appendix 21.9
- Assessment of ECOG performance score
- Assessments of constitutional symptoms
- Physical examination to assess the lymph nodes, spleen and liver
- Clinical staging using Rai and /or Binet as defined per the iwCLL guidelines for diagnosis and treatment of CLL (Hallek, 2008) in Appendix 21.4
- 12-lead ECG
- Peripheral blood smear, bone marrow aspirate and bone marrow biopsy (reference samples) for central pathology reviewer (local pathology results will also be captured on the eCRFs).
- Peripheral blood for disease confirmation by immunophenotyping per Hallek, 2008.

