Operationally the study will proceed as follows: Subjects will be randomized to one of the three treatment arms. The first interim analysis (toxicity only) will be performed once 18 subjects complete one 28-day cycle.

Subsequent

interim analyses will occur at 13-week intervals to monitor both combined toxicity and disease progression. Depending on the calculated posterior probability of toxicity and disease progression, any one of the three treatment arms may be dropped for excessive toxicity or progression rate.

Safety Analysis

All subjects who receive at least 1 dose of study drug will be included in the safety analyses. AEs, vital sign measurements, clinical laboratory information, and concomitant medications will be tabulated and summarized for each treatment arm during therapy. Subject incidence rates of all AEs (including serious, Grade 3, Grade 4, treatment-related [with and without discontinuation] and events requiring the discontinuation of investigational product), will be tabulated by system class, preferred term, and severity using MedDRA terms and by NCI CTCAE Version 3.0, with modifications recommended by the iwCLL guidelines for the diagnosis and treatment of CLL (Hallek, 2008), and by the Cairo-Bishop grading system for TLS. Time to first dose reduction will be summarized for each regimen.

Death and clinically important AEs (including TFR, TLS, second primary malignancies and thrombosis) will also be summarized.

All other measurements will be summarized using means, standard deviations, medians, minimum, and maximum. Graphical displays will be provided where useful in the interpretation of results.

Efficacy Analysis

Efficacy analyses will be performed on the intent-to-treat (ITT) population that includes all subjects randomized.

Response, duration of response, TTR, TTP, EFS, PFS, and OS will be summarized. The Kaplan-Meier procedure will be used to characterize the time-to-event curves in these analyses when there is censoring.

Exploratory Analysis

Pharmacokinetics Analysis

If the data are sufficient, noncompartmental PK parameters, such as T_{max} , C_{max} , AUC, CL/F, and $t_{1/2}$, will be estimated. Descriptive statistics will be provided for plasma concentrations and PK parameters. Lenalidomide concentration data obtained from all visits may be used to develop the population PK model. The relationship between pharmacokinetics and response (biomarkers or clinical outcomes as appropriate) will be explored.

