9.2. Subject Exclusion Criteria

Subjects must not meet any of the following exclusion criteria to be eligible for enrollment into the study:

- 1. Any serious medical condition, laboratory abnormality, or psychiatric illness that would prevent the subject from signing the informed consent form
- 2. Active infections requiring systemic antibiotics
- 3. Systemic treatment for B-cell CLL within 28 days of initiation of lenalidomide treatment
- 4. Alemtuzumab therapy within 60 days of initiating lenalidomide treatment
- 5. (removed in protocol amendment #3)
- 6. Prior therapy with lenalidomide
- 7. History of grade 4 rash due to prior thalidomide treatment
- 8. Planned autologous or allogeneic bone marrow transplantation

- 9. Pregnant or lactating females
- 10. Central nervous system (CNS) involvement as documented by spinal fluid cytology or imaging. Subjects who have signs or symptoms suggestive of leukemic meningitis or a history of leukemic meningitis must have a lumbar puncture procedure performed within two weeks prior to initiating study drug
- 11. Prior history of malignancies, other than CLL, unless the subject has been free of the disease for ≥5 years. Exceptions include the following:
 - Basal cell carcinoma of the skin
 - Squamous cell carcinoma of the skin
 - Carcinoma in situ of the cervix
 - Carcinoma in situ of the breast
 - Carcinoma in situ of the bladder
 - Incidental histologic finding of prostate cancer (TNM stage of T1a or T1b)
- 12. History of renal failure requiring dialysis
- 13. Known Human Immunodeficiency Virus (HIV), Hepatitis B Virus (HBV) and/or Hepatitis C Virus (HCV) infection
- 14. Evidence of TLS per the Cairo-Bishop definition of laboratory TLS (subjects may be enrolled upon correction of electrolyte abnormalities)
- 15. Any of the following laboratory abnormalities:
 - Calculated (method of Cockroft-Gault) creatinine clearance of <60 mL/min (creatinine clearance may also be obtained by the 24-hour collection method at the investigator's discretion)
 - Absolute neutrophil count (ANC) $\leq 1,000/\mu L (1.0 \text{ X } 10^9/L)$
 - $-\quad Platelet\ count \leq 50,\!000/\mu L\ (50\ X\ 10^9/L)$
 - Serum aspartate aminotransferase (AST)/serum glutamic-oxaloacetic transaminase (SGOT) or alanine transaminase (ALT)/serum glutamate pyruvate transaminase (SGPT) > 3.0 x upper limit of normal (ULN)
 - Serum total bilirubin > 1.5 x ULN
- 16. Uncontrolled hyperthyroidism or hypothyroidism
- 17. Venous thromboembolism within 12 months

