		 Resume lenalidomide (at the next lower dose level) when the TLS resolves to Grade 0.
		 If lenalidomide is resumed prior to the start of the subsequent cycle, a chemistry test should be performed every other day for the first week following re-initiation of lenalidomide.
		 Re-escalation to the next consecutive dose level is permitted after completion of one full cycle without laboratory TLS or ≥ Grade 1 TLS, or occurrence of toxicities requiring dose interruption/reduction.

Table 5: Dose Reduction and Modification Guidelines for Lenalidomide (Continued)

Toxicity	Severity	Action
Liver Function Tests (LFTs) Liver Function	ALT > 3.0 and ≤ 5.0 x ULN and serum total bilirubin ≤ 1.5 x ULN ALT > 3.0 and ≤	Continue current dose level Test at next scheduled visit Interrupt levelidemide thereby
Tests (LFTs)	5.0 x ULN and a serum total bilirubin > 1.5 x ULN OR ALT > 5.0 x ULN OR Serum total bilirubin > 1.5 x ULN	 Interrupt lenalidomide therapy. Evaluate ALT and serum total bilirubin weekly until both return to baseline levels Resume lenalidomide when ALT and serum total bilirubin return to baseline. Maintain dose level if recovery from event occurs ≤ 14 days from initial test result. Decrease by one dose level if recovery from event is prolonged > 14 days but ≤ 28 days from initial test result. Continue to monitor weekly LFTs during this cycle. If the event does not repeat, dose escalation or reescalation may continue according to protocol. Medical monitor must be notified if values do not return to baseline within 28 days of the initial event.
Other lenalidomide- related non- hematologic AEs	≥ Grade 3	 Interrupt lenalidomide therapy. May resume lenalidomide when the adverse event resolves to ≤ Grade 2 (decrease one dose level or maintain dose level per the investigator's discretion)

Lenalidomide dose may be interrupted/modified per the investigator's discretion for any AE (any Grade) not outlined in Table 5.

Dose escalation or re-escalation may begin on the scheduled Day 1 of a new cycle according to the protocol guidelines if toxicities requiring dose interruption and/or modification have resolved as specified in Table 5.

If there is a dose interruption during a cycle that lasts beyond Day 28 of the cycle, the subject must still have assessments as per Table 2 every 28 days. An unscheduled visit may be conducted to meet this requirement.

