10.4.1. Prophylaxis and/or Treatment for TLS, TFR, Neutropenia, and Thromboembolic Events

10.4.1.1. Tumor Lysis Syndrome (TLS) Prophylaxis

TLS prophylaxis, comprising of oral hydration and allopurinol 300 mg/day will be initiated at least 3 days prior to starting study drug and for a minimum of the first 3 treatment cycles. For subjects with known allergy to allopurinol prior to study initiation or for those who develop an allergy during the course of study, the medical monitor should be contacted. To maintain fluid intake, subjects must be instructed to drink 8 to 10 eight ounce (240 mL) glasses of water each day for the first 14 days of each cycle during the dose escalation period. Hydration levels should be adjusted according to age and clinical status, and lowered if the subject's cardiovascular status indicates the possibility of volume overload.

Subjects will be monitored for TLS as follows:

- On Day 2 and 4 and then weekly (Days 8, 15, 22) for cycle 1 and the first cycle of each dose escalation
- On Day 1, 8 and 15 of cycle 2 (if not dose escalated)
- At least every 28 days thereafter and as clinically indicated.

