21.3. Cairo-Bishop Definition and Grading of Tumor Lysis Syndrome (Cairo, 2004)

Cairo-Bishop Definition of Laboratory Tumor Lysis Syndrome (LTLS)

Uric Acid	\geq 476 µmol/l (\geq 8.0 mg/dl) or 25% increase from baseline	
Potassium	\geq 6.0 mmol/l (\geq 6.0 mEq/l) or 25% increase from baseline	
Phosphorous	\geq 1.45 mmol/l (\geq 4.5 mg/dl) or 25 % increase from baseline	
Calcium	\leq 1.75 mmol/l (\leq 7.0 mg/dl) or 25% decrease from baseline	ON

Laboratory tumor lysis syndrome (LTLS) is defined as either a 25% change or level above or below normal, as defined above, for any two or more serum values of uric acid, potassium, phosphate, and calcium within 3 days before or 7 days after the initiation of chemotherapy. This assessment assumes that a patient has or will receive adequate hydration (\pm alkalinization) and a hypouricaemic agent(s).

Cairo-Bishop Definition of Clinical TLS

The presence of laboratory TLS and one or more of the following criteria:

- 1. Creatinine: ≥ 1.5 ULN (age ≥ 12 years or age adjusted)
- 2. Cardiac arrhythmia / sudden death
- 3. Seizure*

ULN, Upper limit of normal

Cairo-Bishop Grading System for TLS

Grade	LTLS	Creatinine	Cardiac Arrythmia	Seizure
0	-	≤1.5 x ULN	None	None
1	+	1.5 x ULN	Intervention not indicated	None
2	+	> 1.5 – 3.0 x ULN	Non-urgent medical intervention indicated	One brief generalized seizure; seizure(s) well controlled or infrequent; focal motor seizures not interfering with ADL
3	ţC)	> 3.0 – 6.0 x ULN	Symptomatic and incompletely controlled medically or controlled with device	Seizure in which consciousness is altered; poorly controlled seizure disorder; breakthrough generalized seizures despite medical intervention
4	+	> 6.0 x ULN	Life-Threatening	Seizures of any kind that are prolonged, repetitive, or difficult to control
5	+	Death*	Death*	Death*

LTLS, laboratory tumor lysis syndrome; ULN, upper limit of normal; ADL, activities of daily living

^{*}Not directly attributable to a therapeutic agent

^{*}Probably or definitely attributable to clinical TLS

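### Does the 7-day window in the laboratory TLS definition leave later tumor lysis events without a grade?

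*Protocol*

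**What the plan says.** Appendix 21.3 reproduces the Cairo-Bishop definition. Laboratory TLS needs at least two abnormal values among uric acid, potassium, phosphate and calcium, found "within 3 days before or 7 days after the initiation of chemotherapy". Clinical TLS is then "The presence of laboratory TLS and one or more of the following criteria", the criteria being raised creatinine, arrhythmia or sudden death, and seizure. The grading table carries a column for laboratory TLS but none for time of onset.

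Other parts of the protocol use TLS without that window:

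- Section 10.4.1.1 schedules checks "On Day 2 and 4 and then weekly (Days 8, 15, 22) for cycle 1 and the first cycle of each dose escalation", further checks in a cycle 2 without escalation, and checks at intervals of no more than 28 days after that.
- In Table 5 (Section 10.2.3), re-escalation after TLS of Grade 2 or higher is allowed only "after completion of one full cycle without laboratory TLS" or graded TLS.
- Exclusion 14 (Section 9.2) bars "Evidence of TLS per the Cairo-Bishop definition of laboratory TLS". The Synopsis states: "Screening assessments for protocol eligibility will be performed within 28 days prior to initiating study drug".

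On analysis, the Synopsis says "Death and clinically important AEs (including TFR, TLS, second primary malignancies and thrombosis) will also be summarized". SAP 12.1 says TLS is analyzed by the Cairo-Bishop grading. It defines treatment-emergent events as those from first dose to 30 days after last dose. Neither SAP 12.1 nor SAP 5.1.3 mentions the window.

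**The concern.** The published definition assumes a course of chemotherapy with a clear start. Here the drug is taken every day and the dose may rise up to four times, so initiation could mean first dose, each escalation, or restart after an interruption. The protocol does not choose.

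If the window is applied as written, an event found late in a cycle is not laboratory TLS, hence not clinical TLS, hence ungraded. With a first-dose anchor, no event after an escalation could qualify. The arms allow 4, 3 and 2 escalations, so the reading might bear unequally on the arms being compared. What would be at stake is the grade of a named clinically important adverse event under the primary endpoint.

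**Working it through.** The plan gives no figure to reproduce. The check has two parts: how much a literal reading would exclude, and whether the documents support that reading.

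**Part 1: reach of a literal reading**

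Inputs: window from Appendix 21.3; checks on Days 2, 4, 8, 15 and 22 of cycle 1 and of each escalation cycle (Section 10.4.1.1); maximum escalations of 4, 3 and 2 (Section 8.1.6). Assumptions: 28-day cycles, no delays, full escalation.

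- First dose is Day 1, so 7 days after is Day 1 + 7 = Day 8. Day 8 is inside.
- Earliest escalation is Day 1 + 28 = Day 29, which is 29 − 8 = 21 days after the window closes.
- Checks per arm = 5 × (escalations + 1).
- First-dose anchor: only Days 2, 4 and 8 of cycle 1 are inside, so 3 per arm.
- Anchor at first dose and at each escalation: 3 inside and 2 outside (Days 15 and 22) per cycle.

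| Arm | Checks | Outside, first-dose anchor | Outside, each-escalation anchor |
|---|---|---|---|
| 1 (5 mg start) | 5 × 5 = 25 | 25 − 3 = 22 (88%) | 2 × 5 = 10 (40%) |
| 2 (10 mg start) | 5 × 4 = 20 | 20 − 3 = 17 (85%) | 2 × 4 = 8 (40%) |
| 3 (15 mg start) | 5 × 3 = 15 | 15 − 3 = 12 (80%) | 2 × 3 = 6 (40%) |

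These are counts of visits, not of events. They show how far the literal reading would reach, not how many TLS events lie there.

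**Part 2: whether that reading is the plan's**

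- *Table 5.* The full-cycle condition applies to a cycle after the event. Under a first-dose window, laboratory TLS could not exist in any cycle after the first, so the condition would be met automatically and would mean nothing. The TLS rows give different actions by grade and set no time limit. They make sense only if TLS is graded throughout treatment.
- *Monitoring.* Checks on Days 15 and 22, and in escalation cycles, would serve little purpose if nothing found there could be called TLS.
- *Exclusion 14.* Screening may be 28 days before drug, but the Synopsis and Section 12.2 also require eligibility on laboratory results at Study Day 1 before dosing. That check lies within the 3 days before initiation, so this use fits the definition better than it first seems.
- *Severity at source.* Appendix 21.1 requires the investigator to grade the severity of every adverse event, with TLS graded by Cairo-Bishop. SAP 12.1 takes severity as documented on the CRF.
- *Analysis.* SAP 12.1 adopts the grading system. Nothing in it tells a programmer to compare onset day with a window or to delete a recorded grade.

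**What an added SAP sentence would do**

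- If investigators report and grade late TLS, the tables already contain it and the sentence changes nothing.
- If the window stops an investigator from reporting TLS, there is no event to grade and the sentence cannot restore it.

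**The case for a change.** The best case for a change is that the anchor really is undefined, that it sits under the primary endpoint, and that one sentence is cheap. SAP 12.1 also says that adverse events are summarized by worst CTCAE grade, so two programmers might treat an out-of-window event differently. The summary by cycle covers events of interest, a term the SAP does not expressly apply to TLS. Late onset is not hypothetical either: the amendment rationale describes a TLS case on day 45 in the predecessor study, CC-5013-CLL-001.

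Some of this stands. The wording is loose, and TLS is not listed by name for the by-cycle tables. The rest is weaker:

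- The TLS sentence in SAP 12.1 is specific, and SAP 5.1.3 exempts TLS from CTCAE grading. An analyst would follow those over the general sentence whatever the onset day.
- The sponsor called the day-45 event TLS. The documents do not show which definition that study used, but late onset did not prevent the label.
- None of the predecessor cases is shown to follow an escalation: the original design had no escalation period, and both cases in the amended design occurred at the 2.5 mg starting dose.
- A table by dose level at onset is a separate request that does not arise from the window. Summaries by arm and subject listings are already planned.

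**Conclusion.** The concern does not hold as a fault in the analysis plan. Appendix 21.3 carries over a published time window without adapting it to daily, escalating treatment, and its wording does not match Section 10.4.1.1 or the TLS rows of Table 5. Those passages should agree, and reconciling them is editorial work for the sponsor; no view is taken here on any clinical rule. The analysis does not depend on it, because reported TLS stays in the treatment-emergent tables with its recorded grade.

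The size of any effect is unknown and may be nil. The amendment 6 rationale says that subjects are past the period of TLS risk and that further escalations are not anticipated, so new events that could test the wording are unlikely.

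This rests on two assumptions: that investigators followed the monitoring schedule and Table 5 in recording late TLS, and that programmers take the CRF grade as SAP 12.1 describes. If the first fails, events are missing at source and no SAP wording would bring them back.

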21.4. Grading of Hematological Toxicity (Hallek, 2008)

Grade ^a	Decrease in Platelets ^b or Hb ^c (nadir) From Pretreatment value (%)	Absolute neutrophil count/μL ^d (nadir)		
0	No change to 10%	≥ 2,000		
1	11% - 24%	≥1,500 and < 2,000		
2	25% - 49%	≥1,000 and < 1,500		
3	50% - 74%	≥ 500 and < 1,000		
4	≥ 75%	< 500		

- a.Grades: 1, mild; 2, moderate; 3, severe; 4, life-threatening; 5, fatal. Death occurring as a result of toxicity at any level of decrease from pretreatment will be recorded as grade 5.
- b. Platelet counts must be below normal levels for grades 1-4. If, at any level of decrease the platelet count is $<20,000/\mu\text{L}$, this will be considered grade 4 toxicity, unless a severe or life-threatening decrease in the initial platelet count (e.g., $20,000/\mu\text{L}$) was present pretreatment, in which case the patient is not evaluable for toxicity referable to platelet counts.
- c.Hb levels must be below normal levels for grades 1-4. Baseline and subsequent Hb determinations must be performed before any given transfusions. The use of erythropoietin is irrelevant for the grading of toxicity, but should be documented.
- d. If the absolute neutrophil count (ANC) reaches less than 1,000/μL, it should be judged to be grade 3 toxicity. Other decreases in the white blood cell count, or in circulating granulocytes, are not to be considered, since a decrease in the white blood cell count is a desired therapeutic end point. A gradual decrease in granulocytes is not a reliable index in CLL for stepwise grading of toxicity. If the ANC was less than 1,000/μL prior to therapy, the patient is not evaluable for toxicity referable to the ANC. The use of G-CSF is irrelevant for the grading toxicity, but should be documented.

21.5. ECOG Performance Status Scale

Score	Description
0	Fully active, able to carry on all pre-disease performance without restriction
1	Restricted in physically strenuous activity but ambulatory and able to carry our work of a light or sedentary nature, e.g., light housework, office work.
2	Ambulatory and capable of all self-care but unable to carry out any work activities. Up and about more than 50% of waking hours.
3	Capable of only limited self-care, confined to bed or chair more than 50% of waking hours.
4	Completely disabled. Cannot carry on any self-care. Totally confined to bed or chair
5	Dead

21.6. Clinical Staging of CLL Patients

21.6.1. Rai staging system (modified) (Rai, 1987)

Low-risk disease	Lymphocytosis with leukemia cells in the blood and/or marrow (lymphoid cells > 30%)
Intermediate risk disease	Lymphocytosis, enlarged nodes in any site, and splenomegaly and/or hepatomegaly (lymph nodes being palpable or not)
High risk disease	Disease-related anemia (as defined by hemoglobin level less than 11 g/dl or thrombocytopenia (as defined by platelet count of less than $100 \times 10^9 / L$)

21.6.2. Binet staging system (Binet, 1981)

Staging is based on the number of involved areas, as defined by the presence of enlarged lymph nodes of > 1 cm in diameter or organomegaly, and on whether there is anemia or thrombocytopenia.

Area of involvement considered for staging:

- 1. Head and neck, including the Waldeyer ring (this counts as one area, even if more than one group of nodes is enlarged)
- 2. Axillae (involvement of both axillae counts as one area)
- 3. Groins, including superficial femorals (involvement of both groins counts as one area)
- 4. Palpable spleen
- 5. Palpable liver (clinically enlarged)

Stage A	Hemoglobin \geq 10 g/dL and platelets \geq 100 x 10 ⁹ /L and up to two of the above areas involved
Stage B	Hemoglobin \geq 10 g/dL and platelets \geq 100 x 10 ⁹ /L and organomegaly greater than that defined for stage A (i.e. three or more areas of nodal or organ enlargement)
Stage C	Hemoglobin < 10 g/dL and/or platelet count < 100 x 10 ⁹ /L, irrespective of organomegaly

21.7. **FACT-Leu Questionnaire**

FACT-Leu (Version 4)

	FACT-Leu (Version 4)								
Below is a list of statements that other people with your illness have said are important. By circling one (1) number per line, please indicate how true each statement has been for you during the past 7 days.									
	PHYSICAL WELL-BEING	Not at all	A little bit	Some - what	Quite a bit	Very much	>`		
GP1	I have a lack of energy	0	1	2	3	4	•		
GP2	I have nausea	0	1	2	3	4			
GP3	Because of my physical condition, I have trouble meeting the needs of my family	0	1	2	3	4			
GP4	I have pain	0	1	2	3	4			
GP5	I am bothered by side effects of treatment	0	1	2	3	4			
GP6	I feel ill	0		2	3	4			
GP7	I am forced to spend time in bed	0	1	2	3	4			
_	SOCIAL/FAMILY WELL-BEING	Not at all	A little bit	Some- what	Quite a bit	Very much			
GS1	I feel close to my friends	0	1	2	3	4			
GS2	I get emotional support from my family	0	1	2	3	4			
GS3	I get support from my friends	0	1	2	3	4			
GS4	My family has accepted my illness	0	1	2	3	4			
GS5	I am satisfied with family communication about my illness	0	1	2	3	4			
GS6	I feel close to my partner (or the person who is my main support)	0	1	2	3	4			
Q1	Regardless of your current level of sexual activity, please answer the following question. If you prefer not to answer it, please check this box and go to the next section.								
GS7	I am satisfied with my sex life	0	1	2	3	4			

2/8/2005 Page 1 of 4

FACT-Leu (Version 4)

By circling one (1) number per line, please indicate how true each statement has been for you during the past 7 days.

	EMOTIONAL WELL-BEING	Not at all	A little bit	Some - what	Quite a bit	Very much
GE1	I feel sad	0	1	2	3	4
GE2	I am satisfied with how I am coping with my illness	0	1	2	3	4
GE3	I am losing hope in the fight against my illness	0	1	2	3	4
GE4	I feel nervous	0	1	2	3	4
GE5	I worry about dying	0	1	2	3	4
GE6	I worry that my condition will get worse	0	2	2	3	4

FUNCTIONAL WELL-BEING	Not at all	A little bit	Some - what	Quite a bit	Very much
I am able to work (include work at home)	0	1	2	3	4
My work (include work at home) is fulfilling	0	1	2	3	4
I am able to enjoy life	0	1	2	3	4
I have accepted my illness	0	1	2	3	4
I am sleeping well	0	1	2	3	4
I am enjoying the things I usually do for fun	0	1	2	3	4
I am content with the quality of my life right now	0	1	2	3	4

GF2

GF3

GF4

GF5

FACT-Leu (Version 4)

By circling one (1) number per line, please indicate how true each statement has been for you during the past 7 days.

		ADDITIONAL CONCERNS	Not at all	A little bit	Some - what	Quite a bit	Very much
l	BRM 3	I am bothered by fevers	0	1	2	3	4
	P2	I have certain parts of my body where I experience significant pain	0	1	2	3	4
l	BRM 2	I am bothered by the chills	0	1	2	3	4
l	ES3	I have night sweats	0	1	2	3	4
	LEU 1	I am bothered by lumps or swelling in certain parts of my body (e.g., neck, armpits, or groin)	0	1	2	3	4
l	THI	I bleed easily	0	1	2	3	4
l	TH2	I bruise easily		1	2	3	4
l	HI 12	I feel weak all over	0	1	2	3	4
l	BMT 6	I get tired easily	0	1	2	3	4
	C2	I am losing weight	0		2	3	4
l	C6	I have a good appetite	0	1	2	3	4
l	An7	I am able to do my usual activities	0	1	2	3	4
l	N3	I worry about getting infections	0	1	2	3	4
l	LEU 5	I feel uncertain about my future health	0	1	2	3	4
l	LEU 6	I worry that I might get new symptoms of my illness		1	2	3	4
l	BRM 9	I have emotional ups and downs	0	1	2	3	4
	LEU 7	I feel isolated from others because of my illness or treatment	0	1	2	3	4

2/8/2005 Prog. 2 of 4

